Protocol

N-3 FATTY ACID REQUIREMENTS FOR HUMAN DEVELOPMENT

**DR. [name]
DEPARTMENT OF PEDIATRICS
UNIVERSITY OF BRITISH COLUMBIA**

Study Objectives

Compare the effects on CNS maturity, language and cognitive development, growth, and essential fatty acid status as well as serum parameters in term infants following maternal supplementation during gestation. The study supplements are:

- 1) Single cell triglyceride capsules to provide about 400mg 22:6n-3 containing an orange flavor.
- 2) Soybean/corn oil as placebo capsules containing an orange flavor.

I. CNS maturity:

Compare CNS maturity and infant blood lipid 22:6n-3 with and without an increase in the maternal intake of 22:6n-3 of 400mg/day. Compare EEG maturity, ABR amplitude and latency 48-72 hr, 3 months of age, as well as looking acuity at 2, 3 and 12 months of age.

II. Language development:

Compare speech perception at 9 months and vocabulary comprehension and production at 14 and 18 months.

III. Sleep/Wake patterns:

Compare sleep/wake cycles over a 48-hour period from weeks 4 to 8, and over a 24-hour period at weeks 10, 12, 16 and 18.

IV. Cognitive and behavioral development:

Compare infant mental and physical development at 9 months and 18 months of age and behavioral development at 6, 12 and 18 months of age.

V. Growth:

Compare growth by measuring participants weight, length and head circumference at birth, then at 1,2,3,6,9, and 18 months using standardized procedures.

VI. Nutrient intake of mothers and infants:

Compare energy, fat and nutrient intake of mothers by using a food frequency questionnaire along with a weighed 3-day record at 16 and 36 week gestation. Compare nutrient intake of infants using a feeding diary every month and an infant food frequency questionnaire at 9 & 18 months of age.

VII. Lipid and fatty acid analysis:

Compare maternal blood collected at 16 and 36 weeks gestation and infant blood at 2 months for fatty acid analysis. Compare fetal cord blood and umbilical cord tissue following delivery of the infant. Compare human milk from breast-feeding mothers at 1, 2 and 3 months post-partum.

Study design

I. Description of study:

This will be a randomized, blinded, prospective study with 2 groups; placebo group and supplemented group with 22:6n-3. Women will be enrolled and randomized by 16 weeks gestation. An initial dietary assessment will be done and blood will be collected at 16 weeks. The dietary supplementation will then commence and continue until delivery. The dietary assessment and maternal blood sample will be repeated at 36 weeks gestation. Hospital registration charts will be marked to indicate the women who are participants in this research, and will contain a copy of the informed consent. Following delivery, fetal cord blood and umbilical cord tissue will be collected. Length of gestation, newborn infant weight, length, head circumference and gender will be recorded. The mother-infant pairs will be followed for 18 months following delivery.

To account for drop-outs, approximately 200 mothers per group will be randomized in order to have 120 participants per group.

II. Primary/Secondary Endpoints

Primary: Infant CNS maturity

Secondary: language development, sleep-wake cycle and crying behavior, cognitive and behavioral development, growth (weight, length, head circumference), maternal lipid and fatty acid analysis, gestation length and incidence of prematurity.

Selection of participants

I. Study population:

Acceptable participants will be identified from the registrations for low-risk delivery at the BC Women's Hospital and through advertising. Eligible participants will be 20-40 years of age, 12-16 weeks gestation, expected to deliver a single full-term (37-42 weeks) infant.

II. Participant Exclusion Criteria

All mothers:

- Diabetes
- Cardiac disease
- Renal disease
- Tuberculosis
- HIV/AIDS
- Hepatitis
- Previous pregnancy complications
- Substance abuse

III. Randomization

Participants will be randomized to the supplements using a random number system. The supplements will be given as 2x500mg capsules of single cell triglycerides to provide about 400 mg 22:6n-3, or soybean/corn oil as a placebo. The supplements and placebo capsules will be provided in prepackaged sealed containers for dispensing and will both contain an orange flavor to assist in further blinding. The capsules will be dispensed at 16, 26 and 36 weeks. The number of capsules remaining in each vial will be recorded, and used with the number dispensed, to calculate the number taken by each subject.

Investigational Plan

Study Procedures and Observations

Study visits will occur when the participants are at 16 and 36 weeks gestation, and at 1, 2, 3, 6, 9, 12, 14 & 18 months postpartum.

Study visit 1 (16 weeks gestation)

- Informed consent – At or prior to this visit, the participant who meets all of the applicable inclusion criteria and none of the exclusion criteria will be contacted and the study will be explained to them. Their questions will be answered to their satisfaction. After giving time for consideration, the participant will be asked to grant permission for their infant and themselves to participate in the study. If permission is granted, an informed consent form will be signed by the participant and a copy of the signed consent written informed consent form will be provided to them.
- Verify inclusion and exclusion criteria.
- Randomization.
- Dispense supplements.
- Dietary assessment (Food frequency of prior 4 weeks + weighed 3 day food record)
- Maternal blood sample.

Study days 16 – 36 weeks gestation

- Periodic phone calls to participant.
- Dispense supplements.

Study visit 2 (36 weeks gestation)

- Dietary assessment (Food frequency of prior 4 weeks + weighed 3 day food record).
- Maternal blood sample.
- Dispense supplements.

Study days 36 weeks gestation – Day of delivery

- Periodic phone calls to participant.

Day of delivery (37 – 42 weeks gestation)

- Fetal cord blood collection.
- Anthropometric measurements of newborn (body weight, body length and head circumference).
- CNS maturation measures at 48-72 hr (EEG and ABR).

Study visit 3 (1 month postpartum)

- Breast-milk collection (breast-feeding mothers).
- Anthropometric measurements of infant (body weight, body length and head circumference).
- Infant feeding diary.

Study visit 4 (2 months postpartum \pm 2 days)

- Breast-milk collection (breast-feeding mothers).
- Anthropometric measurements of infant (body weight, body length and head circumference).
- Looking acuity assessment.
- Infant feeding diary.

Study visit 5 (3 months postpartum \pm 2 days)

- Breast-milk collection (breast-feeding mothers).
- Anthropometric measurements of infant (body weight, body length and head circumference).
- CNS maturation measures (EEG and ABR).
- Looking acuity assessment.
- Infant feeding diary.

Study months 4 & 5 postpartum

- Infant feeding diary.
- Periodic phone calls to participant.

Study visit 6 (6 months postpartum \pm 2 days)

- Anthropometric measurements of infant (body weight, body length and head circumference).
- Infant characteristic questionnaire - ICQ (Bates)
- Infant feeding diary.

Study months 7 & 8 postpartum

- Infant feeding diary.
- Periodic phone calls to participant.

Study visit 7 (9 months postpartum \pm 3 days)

- Anthropometric measurements of infant (body weight, body length and head circumference).
- Infant food frequency questionnaire (dietary intake).
- Language development (speech perception).
- Mental development (2 step problem solving)

Study months 10 & 11 postpartum

- Infant feeding diary.
- Periodic phone calls to participant.

Study visit 8 (12 months postpartum \pm 5 days)

- Looking acuity assessment.
- Infant behavior questionnaire – IBQ (Rothbart)
- Infant feeding diary.

Study month 13 postpartum

- Infant feeding diary.
- Periodic phone calls to participant.

Study visit 9 (14 months postpartum)

- Language development (MacArthur CDI, infant version).
- Infant feeding diary.

Study months 15 to 17 postpartum

- Infant feeding diary.
- Periodic phone calls to participant.

Study visit 10 (18 months postpartum \pm 5 days)

- Anthropometric measurements of infant (body weight, body length and head circumference).
- Infant food frequency questionnaire (dietary intake).
- Language development (MacArthur CDI, infant & toddler version).
- Early childhood behavior questionnaire – ECBQ (Bates)
- Bayley's Scales of Childhood Development (II).

Methods to assess study endpoints

1) Central Nervous System maturity

Electrophysiological measures, such as EEG and auditory evoked brain stem responses, will be used to assess the effects of 22:6n-3 on CNS maturation. All recordings will use routine scalp electrodes, and record per standard protocol.

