This form will document if the participants completed the study (visit 10) and if not, the reason for withdrawing from the study including the date of the last study visit.

Investigational product

The study supplements for the participants enrolled in this study will be provided in a capsule form.

These study supplements will be supplied by Martek Bioscience Corp:

- Single cell triglyceride capsules to provide about 400mg 22:6n-3.
- Soybean/corn oil as placebo capsules

The 22:6n-3 and placebo capsules will be provided in prepackaged sealed containers for dispensing. The participants will be randomized to the supplements using a random code number system. The study supplements will contain an orange flavor to assist in further blinding. The number of unused capsules will be recorded at 26 weeks gestation, 36 weeks gestation and after delivery in order to calculate the total number taken by each subject.

Duration of use

Study supplement usage is from 16 weeks gestation to day of delivery.

Statistics

Sample size

The calculation of sample size is based on the measures of CNS maturity of language development, VEP visual acuity and Bayley Scales, rather than the biochemical determinants, which will require a smaller sample size of <30 per group. Sample sizes were estimated for VEP acuity, language development at 9 and 14 months using the non-native consonant recognition and CDI, and Bayley Scales at 18 month. EEG was not included since there is no baseline information on which to estimate the difference or variability. Taking into account the multiple outcomes using the Bonferroni correction, the largest sample size required is 120/group with a corrected α of 0.05 and power of 80% to detect an effect size equal to half a standard deviation.

Statistical analysis

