Differences in maternal plasma, RBC, fetal umbilical cord plasma and RBC and milk fatty acids between the 2 randomized groups will be determined using one way analysis of variance (ANOVA). One way ANOVA will be used to test for differences in measures of CNS maturity, looking acuity, and language development. Regression analyses will be used to determine the relation between intake (g/day & adjusted for energy intake) of selected fatty acids and the maternal and infant blood, umbilical tissue and milk 20:4n-6, 20:5n-3 and 22:6n-3. A stepwise multiple regression will be used to predict independent factors, including gender, maternal smoking and alcohol intake (as appropriate), highest level of education attained by the mother, family income, birth order, ethnic background, and maternal weight gain in pregnancy, maternal dietary

variables, and duration of breast-feeding, associated with the developmental outcomes. The measures of weight, length and head circumference will be used to plot growth curves for each infant, then an imputation procedure used to estimate weight, length, head circumference and rate of growth from birth to exactly 4, 6, 9 and 18 month for each infant.

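### With about 40% overall loss allowed for, the group comparison is an unadjusted one-way ANOVA that ignores baseline predictors and earlier outcomes and is exposed if prognosis-related loss differs by arm

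*Protocol*

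**What the plan says.** Under Study design, Description of study, the recruitment target is inflated for a stated reason, "To account for drop-outs": "approximately 200 mothers per group will be randomized in order to have 120 participants per group". No rate by visit, timing or split by arm is given. Follow-up runs to 18 months after delivery.

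Under Statistics, Statistical analysis, the between-group test is fixed: "One way ANOVA will be used to test for differences in measures of CNS maturity, looking acuity, and language development". The same method is named for the fatty acid comparisons. It is not named for the Bayley Scales, sleep or behaviour.

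Predictors of development appear only in a separate stepwise regression that looks for factors associated with the developmental outcomes. Its candidates include "highest level of education attained by the mother, family income, birth order, ethnic background, and maternal weight gain in pregnancy", with duration of breast-feeding also listed. The protocol does not say that this regression includes treatment arm. Imputation is mentioned only for growth, to obtain values at exact ages.

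Several outcomes are measured more than once (Study Objectives; Study Procedures and Observations): EEG and ABR at 48-72 hours and 3 months, looking acuity at 2, 3 and 12 months, and the infant CDI at 14 and 18 months. Maternal blood for fatty acids is drawn at 16 weeks, before supplementation begins.

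**The concern.** The protocol fixes both a large allowance for loss and a test poorly suited to it. A one-way ANOVA at a given age compares the infants who have a value at that age and conditions on nothing else. If the infants who remain differ in prognosis between the arms, the test cannot tell that difference from an effect of the supplement, in either direction. An infant with acuity measured at 2 and 3 months but lost by 12 months contributes nothing to the 12-month comparison, although the earlier values carry information about the missing one.

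Leaving out baseline predictors also gives up whatever precision they would bring, even if loss is harmless. The ANOVA covers the primary endpoint, infant CNS maturity, so this is not confined to secondary outcomes.

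**Working it through.** **1. The planned loss.** From the protocol: 200 randomised and 120 retained per group. Loss = 1 − 120/200 = 0.40. In reverse, 120/(1 − 0.40) = 200, so the two figures agree. (The 120 itself is a separate matter: 0.5 SD, 80% power and two-sided alpha 0.05 give 63 per group, and Bonferroni over the four outcomes named for sizing gives 90. Nothing below depends on this.)

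**2. When loss biases the ANOVA.** Let m be the share missing in an arm and δ the completer mean minus the drop-out mean, in SD. The full-arm mean is (1 − m)·C + m·D = C − mδ, where C and D are the completer and drop-out means. Completers therefore overstate their arm by mδ, and the difference between arms is biased by

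bias = m₁δ₁ − m₂δ₂.

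This is zero whenever m and δ match across arms, however large δ is. The protocol gives neither δ nor m by arm, so the values below are assumptions:

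| Assumed loss (arm 1, arm 2) | Assumed δ (arm 1, arm 2) | Bias, SD |
|---|---|---|
| 40%, 40% | 0.5, 0.5 | 0.20 − 0.20 = 0 |
| 35%, 45% | 0.5, 0.5 | 0.175 − 0.225 = −0.05 |
| 40%, 40% | 0.5, 0.25 | 0.20 − 0.10 = 0.10 |
| 40%, 40% | 0.5, 0 | 0.20 − 0 = 0.20 |

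**3. Effect on the error rate.** With 120 per group and no true effect, the noncentrality is bias × √(120/2) = 7.746 × bias. That is 0.387, 0.775 and 1.549 for biases of size 0.05, 0.10 and 0.20. The noncentral t on 238 degrees of freedom, two-sided 5%, gives rejection rates of 6.7%, 12.0% and 33.9%.

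**4. Effect on power.** A bias of 0.10 SD towards zero turns the 0.5 SD target into 0.4 SD. At 120 per group and alpha 0.05/4 = 0.0125, power falls from 91% to 72%.

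**5. Check by simulation.** Assumptions: one baseline predictor with correlation r to the outcome, 40% loss in each arm unless stated, retention log-odds changing by 0.7 per SD of the predictor, no true effect, and error evaluated at 120 per group.

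| Loss mechanism | r | Size of unadjusted bias, SD | Error rate |
|---|---|---|---|
| Same in both arms | 0.5 | about 0 | 5% |
| Same slope, loss 50% v 30% | 0.5 | 0.06 | 8% |
| Related to predictor in one arm only | 0.3 | 0.08 | 9% |
| Related to predictor in one arm only | 0.5 | 0.13 | 17% |
| Related to predictor in one arm only | 0.7 | 0.18 | 29% |

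Adjusting for the predictor brings the bias to about 0 in every row. It does so because loss was made to depend only on that predictor.

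**6. Precision.** Covariates with multiple correlation r to the outcome leave residual variance of about 1 − r². That is 0.91 for r = 0.3, 0.75 for r = 0.5 and 0.51 for r = 0.7. The protocol gives no r, so the gain is unknown. It could be small.

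**The case against.** The strongest reply is that a randomised comparison without covariates is valid, and that nothing in the protocol shows loss will differ by arm. The trial is blinded, both capsules are orange-flavoured and come in sealed containers, and supplementation stops at delivery, so much of the follow-up takes place after treatment. The larger figures above need the gap between completers and drop-outs to differ sharply between arms. A ten-point difference in loss rate alone gives only 0.05 SD and about 7% error. All of this stands, and it limits the point to a risk.

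A reader might infer that the ANOVA is unbiased only if loss is unrelated to outcome. The documents do not support that, and the first rows of both tables contradict it. With no effect, bias needs a rate or mechanism that differs by arm. With a true effect, loss that depends on the outcome itself can also bias the comparison.

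A reader might also take 40% as the loss at every test. It is one overall allowance with an approximate starting number. Loss builds up over time, so it may be lower at the 48-72 hour and 3-month measures.

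Nor can one conclude that missing data will go unhandled. Analysis sets and imputation may be set out in an analysis plan that is not at hand. The protocol does, however, name the unadjusted test for these outcomes, and that choice is open to comment.

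The remedy also has limits. Mothers lost before delivery have no infant outcome, so a repeated-measures model recovers nothing for them.

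**Conclusion.** The point holds as a poor fit between two things the protocol fixes: a 40% overall allowance for loss and an unadjusted one-way ANOVA for CNS maturity, looking acuity and language. The ANOVA is at risk of bias if prognosis-related loss differs between arms, and it gives up the precision that baseline predictors and earlier outcomes could supply. Bias is not shown to exist.

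On the assumed inputs, plausible sizes run from zero to 0.20 SD, against a target of 0.5 SD. The corresponding error rates for a nominal 5% test run from 5% to about 34% at 120 per group. The upper end rests on arm-specific drop-out gaps that the documents neither state nor imply. The change is worth making because it costs little and rests on a weaker assumption about loss.

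**What to change.** In Statistics, Statistical analysis, for CNS maturity, looking acuity and language:

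- Replace the one-way ANOVA with a linear model of arm plus a short prespecified set of pre-randomisation covariates: maternal education, family income, birth order, ethnic background and 16-week maternal 22:6n-3. The visit schedule does not say when the first four are recorded; the 16-week visit would make them available for every mother randomised.
- Leave post-randomisation variables, such as pregnancy weight gain and breast-feeding duration, out of this model. They can stay in the exploratory stepwise regression.
- Where an outcome is repeated (EEG/ABR at 48-72 hours and 3 months, acuity at 2, 3 and 12 months, infant CDI at 14 and 18 months), use a likelihood-based repeated-measures model with the same covariates, so that earlier values inform later missing ones.
- Keep the unadjusted ANOVA as a sensitivity analysis.

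The cost is more analysis work, with no new participants, visits or tests. The result relies on data being missing at random given the modelled variables. That is weaker than what the ANOVA needs, but it still cannot be verified from the data.

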Speech perception is based on the ability of the infant to discriminate fine phonetic differences that distinguish syllables in the native and an unfamiliar language. This procedure involves conditioning the infant to provide an operant head-turn in response to a change in phonetic category within a series of speech stimuli. The infants will be tested in a sound attenuated chamber first on their ability to discriminate English voiced bilabial versus alveolar phones, followed by a non-English (Hindi) retroflex versus dental phonetic contrast. The Hindi language distinguishes four places of articulation (bilabial, dental, retroflex and velar), while the English language distinguishes 3 (bilabial, alveolar and velar). The test will be administered with the guidance of Dr [name]. Data will be recorded for all infants of 9 months of age, but not analyzed for infants exposed to Hindi in their home environment.

MacArthur CDI for infants and toddlers

The MacArthur CDI is a standardized parent report instrument designed to gather information on the infant's vocabulary comprehension and production. The infant version (words and gestures) has been developed and validated for infants 8 to 16 months of age and includes 396 words. The toddler version (words and sentences) is for infants 16 to 30 months of age. We will administer the infant CDI at 14 months postpartum and both the infant and toddler CDI at 18 months postpartum. The CDI results will be scored for the raw number of words, and the percentile scores for each age and gender (girls tend to be slightly advanced in gender).

3) Cognitive development

The Bayley Scales of Infant Development II, a standardized test of infant development, will be given at 18 months postpartum, with the mental development index (MDI) and psychomotor development index (PDI) standardized for age, based on reference norms. The MDI score is derived from the total number of items correctly performed, regardless of skill or weakness in any particular area. The Bayley Scales II, however, includes clusters of items (Facets) for the mental scale that provides information on language, cognitive and visual-motor abilities. Scores for each facet will be quantified as the ratio of correct items to the total number of items in the Facet as described by [name]. Scores on the Facets at 18 months of age are related to cognitive, verbal and visual-motor function at 4 – 5 years of age assessed with the Wechsler Preschool and Primary Scale of Intelligence. Dr. [name], who has extensive experience with the Bayley Scales, will collaborate. The test will be given by a trained tester, with equipment and procedures. We will test at 18 months because the range of tasks that can be completed is greater than at younger ages, thus allowing a greater sensitivity to discriminate differences among infants.

4) Blood, tissue and milk samples

Blood will be drawn via venipuncture for a fatty acid profile from all mothers at 16 and 36 weeks gestation. A total of 3.0 ml of blood is needed for each blood draw. Fetal cord blood will be collected following delivery of the infant.

Breast-milk samples will be collected from all breast-feeding mothers at 1 and 2 months postpartum. The mothers will be instructed not to collect milk during the first 2 – 5 minutes of a feed (fore-milk), or drip milk, then interrupt the infant and gently express about 10 ml of human milk into the vial provided. The mother should label the vial with the date the sample was obtained. Samples will be frozen following collection, transported on ice and stored at -80 C on receipt at the lab.

5) Body weight

Birth weight will be obtained from the participant's birth records or directly from the parent/care giver, if the record is not available to the Investigator.

During the study period, infants will be weighed one time at each visit without clothing or diaper, on a standard pediatric balance, to the nearest gram. All balances will be checked to register the same weights throughout the range of weights expected.

6) Body length

Body length at birth will be obtained from the infant's birth records or directly from the parent/care giver, if the record is not available to the Investigator.

Body length for the study period will be measured 1 time at each visit to the nearest millimeter. The infant should be held in a recumbent position with the help of two examiners and a suitable measuring device. One person holds the infant's head into contact with the fixed headboard and a second person holds the infant's feet, toes pointing directly upward and while applying gentle traction, bring the movable footboard to rest firmly against the infant's heels.

7) Head circumference

Head circumference at birth will be obtained from the infant's birth records or directly from the parent/care giver, if the record is not available to the Investigator.

Head circumference for the study period will be measured 1 time at each visit to the nearest millimeter employing a flexible, non-stretchable cloth or vinyl tape. The tape is to be applied firmly around the head above the supraorbital ridges, covering the most prominent part of the frontal bulge anteriorly, and over the part of the occiput that gives maximum circumference.

8) Periodic phone calls

Study personnel will contact the participants periodically between study visits to collect information on diet, tolerance, and adverse events, determine if additional supplements are needed, remind participants of upcoming study visits, and answer questions concerning the study.

9) Maternal dietary intake/Infant dietary intake

At study visits 1 & 2, participants will be asked to complete a food frequency questionnaire of the preceding 4 weeks, together with a weighed 3-day food record. The food frequency questionnaire will be completed using an interview format with a trained dietician, using food models, scales, cups and spoons. Information on the frequency with which the food is eaten, portion size, brand name or place of purchase, methods of preparation, types of margarine, fats and oils, and types of fish and seafood will be collected.

Infant dietary intakes will be recorded using a feeding diary completed each month, and designed to capture when human milk is substituted, juices and solids are introduced and what they are. At study visits 7 and 10, dietary intake will be collected using an infant food frequency questionnaire.

10) Final evaluation

This form will document if the participants completed the study (visit 10) and if not, the reason for withdrawing from the study including the date of the last study visit.

Investigational product

The study supplements for the participants enrolled in this study will be provided in a capsule form.

These study supplements will be supplied by Martek Bioscience Corp:

- Single cell triglyceride capsules to provide about 400mg 22:6n-3.
- Soybean/corn oil as placebo capsules

The 22:6n-3 and placebo capsules will be provided in prepackaged sealed containers for dispensing. The participants will be randomized to the supplements using a random code number system. The study supplements will contain an orange flavor to assist in further blinding. The number of unused capsules will be recorded at 26 weeks gestation, 36 weeks gestation and after delivery in order to calculate the total number taken by each subject.

Duration of use

Study supplement usage is from 16 weeks gestation to day of delivery.

Statistics

Sample size

The calculation of sample size is based on the measures of CNS maturity of language development, VEP visual acuity and Bayley Scales, rather than the biochemical determinants, which will require a smaller sample size of <30 per group. Sample sizes were estimated for VEP acuity, language development at 9 and 14 months using the non-native consonant recognition and CDI, and Bayley Scales at 18 month. EEG was not included since there is no baseline information on which to estimate the difference or variability. Taking into account the multiple outcomes using the Bonferroni correction, the largest sample size required is 120/group with a corrected α of 0.05 and power of 80% to detect an effect size equal to half a standard deviation.

Statistical analysis

Differences in maternal plasma, RBC, fetal umbilical cord plasma and RBC and milk fatty acids between the 2 randomized groups will be determined using one way analysis of variance (ANOVA). One way ANOVA will be used to test for differences in measures of CNS maturity, looking acuity, and language development. Regression analyses will be used to determine the relation between intake (g/day & adjusted for energy intake) of selected fatty acids and the maternal and infant blood, umbilical tissue and milk 20:4n-6, 20:5n-3 and 22:6n-3. A stepwise multiple regression will be used to predict independent factors, including gender, maternal smoking and alcohol intake (as appropriate), highest level of education attained by the mother, family income, birth order, ethnic background, and maternal weight gain in pregnancy, maternal dietary

variables, and duration of breast-feeding, associated with the developmental outcomes. The measures of weight, length and head circumference will be used to plot growth curves for each infant, then an imputation procedure used to estimate weight, length, head circumference and rate of growth from birth to exactly 4, 6, 9 and 18 month for each infant.

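### The CDI is scored and compared without regard to home language, which adds avoidable variance and may dilute an effect; home language should be recorded before supplementation and adjusted for.

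*Protocol*

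**What the plan says.** All references are to the protocol.

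- **Administration (Methods to assess study endpoints, 2) Language development, MacArthur CDI).** The CDI is described as a "standardized parent report instrument designed to gather information on the infant's vocabulary comprehension and production". The infant form has 396 words. On timing: "We will administer the infant CDI at 14 months postpartum and both the infant and toddler CDI at 18 months postpartum".
- **Scoring (same section).** "The CDI results will be scored for the raw number of words, and the percentile scores for each age and gender". Age and gender are the only characteristics taken into account. The language of the form is not stated.
- **The neighbouring test (Speech perception).** Data are recorded for all infants at 9 months "but not analyzed for infants exposed to Hindi in their home environment". This is the only home-language rule in the protocol.
- **Eligibility (Selection of participants).** "Eligible participants will be 20-40 years of age, 12-16 weeks gestation, expected to deliver a single full-term (37-42 weeks) infant". The exclusions are medical or obstetric conditions and substance abuse. Language is not mentioned.
- **Analysis (Statistics, Statistical analysis).** "One way ANOVA will be used to test for differences in measures of CNS maturity, looking acuity, and language development". A separate stepwise regression looks for factors associated with the developmental outcomes. Its candidates include "highest level of education attained by the mother, family income, birth order, ethnic background", but not home language.
- **Sample size (Statistics).** The CDI is one of the outcomes on which the trial was sized, although language development is listed as a secondary endpoint.

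**The concern.** A checklist of fixed words credits an infant only for words that the parent can match to the list. An infant raised mainly in another language may have a normal vocabulary and still score low. For that infant an age-and-gender percentile partly reflects which language is spoken at home.

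The protocol does not restrict entry by language, and its Hindi rule shows that at least some non-English exposure was foreseen. It therefore has a reason to ask about home language, but uses the answer for one of its two kinds of language test only.

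Three things are at stake: extra variance in an outcome that helped to set the sample size, possible dilution of a supplement effect if the form registers it poorly in these infants, and percentiles that cannot be read as vocabulary for part of the sample. Ethnic background does not repair this. It is an imperfect stand-in for language spoken at home, and it enters only the stepwise model, where selection may drop it, not the group comparison.

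**Working it through.** **Inputs from the protocol.** n = 120 per group, effect 0.5 SD, planned power 80%, a Bonferroni-corrected alpha given as 0.05.

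**Assumed inputs (not in the protocol).**
- q, the share of infants raised mainly in a language other than that of the form: 20-30%.
- D, their mean score deficit: 0.5-1.0 SD.
- Per-test alpha 0.05/4 = 0.0125, two-sided. This counts four sizing outcomes: VEP acuity, consonant recognition, CDI and Bayley.

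**The plan's own figure.** With the normal approximation, n per group = 2(z₁₋α/₂ + z₀.₈₀)²/0.5². This gives 63 at alpha 0.05 and 90 at alpha 0.0125; 120 is reached at alpha 0.0025. The stated 120 is thus not reproduced at 0.05 or at 0.0125. That is a separate matter, and 120 is taken as given here.

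**Formulas.**
- Variance factor: V = 1 + q(1−q)D².
- If affected infants register a fraction f of the effect, the standardised effect in an unadjusted comparison is d = 0.5(1 − q + fq)/√V.
- Power is that of a two-sided t-test with 238 degrees of freedom and noncentrality d√(120/2). The small extra variance from unequal effects is ignored.

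With no affected infants, d = 0.5 and power is 91%.

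**Variance factor.**
- q = 0.2, D = 0.5: V = 1 + 0.16 × 0.25 = 1.04; effective n = 120/1.04 ≈ 115.
- q = 0.3, D = 1.0: V = 1 + 0.21 × 1 = 1.21; effective n = 120/1.21 ≈ 99.

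**Power of the unadjusted comparison, all infants.**

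| Effect registered in affected infants | q = 0.2, D = 0.5 | q = 0.3, D = 1.0 |
|---|---|---|
| Full (variance only) | d = 0.500/1.020 = 0.490; 90% | d = 0.500/1.100 = 0.455; 84% |
| Half | d = 0.450/1.020 = 0.441; 82% | d = 0.425/1.100 = 0.386; 68% |
| None | d = 0.400/1.020 = 0.392; 70% | d = 0.350/1.100 = 0.318; 48% |

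**Restricting to infants in the form's language.** This leaves 120 × 0.8 = 96 or 120 × 0.7 = 84 per group. Power for 0.5 SD is 83% or 76%.

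**Adjusting for home language in all infants.** If the covariate captures the whole deficit, V returns to 1 and the numerators above become the standardised effects:
- full effect: d = 0.50, power 91%;
- half effect: d = 0.45 or 0.425, power 83% or 78%;
- no effect: d = 0.40 or 0.35, power 72% or 58%.

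Adjustment recovers the variance loss but not the dilution. Restriction is clearly better only when the form registers well under half the effect in affected infants.

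**The case against.** The strongest reply is that the protocol is silent rather than wrong. It says how forms are scored, not which infants enter the comparison, and outcome-specific analysis sets and covariates can be left to a SAP, which is not at hand. That is fair as to the analysis set. It is weaker as to the method: the protocol itself fixes the scoring, the one-way ANOVA and a language rule for the neighbouring test. Home language must also be asked before supplements start if it is to be a clean baseline variable.

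Second, the Hindi rule has its own purpose: Hindi supplies the unfamiliar contrast in that task. It shows that some exposure was thought possible, not that 20-30% of infants are raised mainly in another language. This stands, so the share can only be assumed.

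Third, a reader might infer three stronger things that the documents do not support.
- **Bias between groups.** Allocation is random and blinded, so low scores should fall about equally in both. A chance imbalance is possible, as for any unmeasured covariate.
- **A power of 48% as the expected result.** That needs the form to register no effect in any affected infant, which sits poorly with a deficit of only 0.5-1.0 SD: such a score is not obviously at the floor.
- **The same fault in the Bayley language facet.** The Cognitive development section does not state the language in which the test is given, so the point has no footing.

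Finally, making the restricted set the main analysis would be a trade-off. If added variance is the only harm, its 83% or 76% is below the 90% or 84% from simply keeping everyone.

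**Conclusion.** The point holds as a design improvement, not as an error that invalidates the comparison. The protocol leaves the CDI unrestricted and unadjusted for home language although it already needs such information for another test.

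On the assumed values of q, D and alpha, the likely minimum cost is small: a fall of 1 to 7 percentage points in power, which stays above the planned 80%. Larger losses depend on how far the form fails to register an effect in affected infants, about which the protocol says nothing. All these figures also assume that the form is in one language, which is not stated. The difficulty with percentiles for infants outside the form's language does not depend on the power assumptions. The recommendation is worth making mainly because it costs so little.

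**What to change.** 1. Record the infant's expected main home language at enrolment, before supplements start, and state the language of the CDI form. The same question can cover Hindi exposure for the rule "not analyzed for infants exposed to Hindi in their home environment".
2. Compare CDI raw scores between groups in all infants with home language as a prespecified covariate, in place of the unadjusted one-way ANOVA for this outcome.
3. Report the comparison restricted to infants whose main home language is that of the form as a prespecified supporting analysis. Because the subset is defined on a baseline variable, it keeps the randomised comparison.
4. Do not interpret CDI percentiles for infants outside the form's language.

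The cost is one enrolment question, one covariate and a few lines of text. No infant is lost from the main CDI comparison.
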